To carry out the study, the hiker was previously registered. The researchers contacted the participants to explain the study. In addition, data on age, sex, foot number and associated diseases that prevented the completion of the route were obtained. One hour before starting the route, researchers who did not intervene in the exploration process, made registration and delivery to each hiker of two technical socks (1 Set and 1 Tierra) appropriate to the size of the foot and randomly for the right foot (RF) and left foot (LF). Likewise, it proceeded for non-technical socks (cotton), but in this case both feet wore the same type of sock. All the participants before the initial exploration had their socks put on for half an hour. The hike was low-difficulty, over a short distance [37]. The first 14.5 km were on asphalt and the last 15.1 km on dirt. The height range was 189 m and the pace was moderate, at 5 km/hour. The sample comprised 109 participants (53 men and 56 women). Two women had to give up the hike for personal reasons. Both wore technical socks.

The Table 1 explain the anthropometric characteristics of the participants and the distribution of the socks, differentiating by sex and feet.

Anthropometric variable	Total	Male	Female	
Gender		48.6%	51.4%	
Age (years)	44± 25	49± 21	36 ± 24	
Height (meters)	1.7± 0.1	1.7± 0.1	1.6± 0.1	

81.0±13.5

61.4±7.8

68.8±19.4

Table 1. Anthropometric variables, total sock distribution and sock distribution by gender.

BM	II	24.9± 3.6	26.6± 3.7	23.5± 9.1
Sock type di	istribution	Total %	Male %	Female %
LF sock	Tierra	40.4 (n=44)	35.8 (n=19)	44.6 (n=25)
	Set	29.4 (n=32)	35.8 (n=19)	23.3 (n=13)
	Cotton	30.2 (n=33)	28.4 (n=15)	32.1 (n=18)
RF sock	Tierra	29.4 (n=32)	35.8 (n=19)	23.3 (n=13)
	Set	40.4 (n=44)	35.8 (n=19)	44.6 (n=25)
	Cotton	30.2 (n=33)	28.4 (n=15)	32.1 (n=18)

Km=Kilometres, n=sample size, %=Percentage, ±=Standard deviation, kg=Kilogrammes, BMI=Body mass index, LF=Left foot, RF=Right foot.

4. Study variables

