Quantitative variables depending on whether the samples were paired or independent, Friedman's test for related samples and Kruskal-Wallis was performed for independent samples, both with Bonferroni correction for multiple testing was applied. For the qualitative variables the

chi-square or Fisher's exact test with a significance level of α = 0.05 was carried out. The variables analysed by logistic regression were quantified using the ODDS Ratio (OR). The effect size for the different variables was also calculated. First, for Kruskall-Wallis tests, the variation was between 0.443 y 0.888, and for Friedman tests, the variation was between 0.336 y 0.623. Therefore, in both cases the effect size could be considered median and high.

All p-values = 0.000 are less than 1 per 1000.

Results

After completing the first part of the hike, the most frequent dermal lesions among participants were blisters and erosions.

Table 3. Prevalence of skin, muscle and nail lesions during the 0-14.5 km of the hike by sex.

(0.14 = 1)				Fen	nale					Ma	ıle		
(0-14.5 km)		Tier	ra %	Se	et %	Cott	on %	Tier	ra %	Set	%	Cott	on %
Skin lesion	%Tt.	RF	LF	RF	LF	RF	LF	RF	LF	RF	LF	RF	LF
Blister	12.8	0.0	4.0	8.0	7.7	22.2	27.8	0.0	5.3	5.3	0.0	6.7	13.3
Erosion	2.8	0.0	0.0	0.0	0.0	11.1	5.6	0.0	0.0	0.0	0.0	6.7	0.0
(0.44.5.1)				Fer	male					Ma	ıle		
(0-14.5 km)		Tier	ra %	Se	et %	Cott	on %	Tier	ra %	Set	%	Cott	on %
Muscle lesion	%Tt.	RF	LF	RF	LF	RF	LF	RF	LF	RF	LF	RF	LF
Pain due inadequate warm	21.1	23.1	27.8	8.0	7.7	27.8	27.8	10.5	15.8	10.5	0.0	13.3	13.3
Inflammation	2.8	0.0	4.2	4.0	0.0	0.0	0.0	0.0	10.5	10.5	0.0	0.0	0.0
Muscle discomfort	1.8	0.0	0.0	0.0	0.00	0.0	0.0	5.3	5.3	0.0	0.0	0.0	0.0

Km=Kilometres, %=Percentage, Tt=Total, RF=Right foot, LF=Left foot.

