None of the other dermal lesions included in the evaluation (reddened skin, urticaria, crevice and heloma) were detected. Significant differences were found between the percentage of dermal lesions in hikers wearing technical socks (6.6%) and non-technical socks (36.4%) (p-value=0.000). The women had a higher percentage of dermal lesions (23.2%) than the men (7.5%) (p-value=0.034), regardless of sock type. Moreover, the percentage of women with dermal lesions was significantly higher among wearers of non-technical socks (50%) than in wearers of technical socks (10.5% had lesion) (p-value=0.002). Particularly the women presented more blisters in both RF and LF when they wore cotton sock compared to the Tierra and Set socks (RF p-value = 0.050, LF p-value = 0.042). In the case of men, there was no difference in any of the skin lesions at 14.5 km on any foot compared to the sock used (Table 3). The most frequent muscle lesions at the end of the first part of the hike were pain due inadequate warm (21.1%), inflammation (2.8%) and muscle discomfort (1.8%). No sprains or nail disorders were detected at the end of the first part of the hike. No difference between any of muscle lesions analyzed and technical and non-technical socks were found. By sex, no differences were found regarding technical and non-technical socks or concerning the model used sock on each foot (Table 3).

Table 4. Prevalence of skin, muscle and nail lesions during the 14.5-29.6 km of the hike by sex.

(14.5-29.6 km)				Fema	ale					N	I ale		
(14.5-29.6 KM)		Tie	rra %	Set	%	Cott	on %	Tier	ra %	Se	et %	Cott	on %
Skin lesion	%Tt.	RF	LF	RF	LF	RF	LF	RF	LF	RF	LF	RF	LF
Blister	19.6	7.7	12.0	20.0	7.7	25.0	12.5	5.3	0.0	5.3	21.1	6.7	0.0
Erosion	7.5	0.0	4.0	8.0	0.0	12.5	18.8	0.0	0.0	0.0	0.0	20.0	13.3
Reddened skin	3.7	0.0	0.0	0.0	0.0	18.8	18.8	0.0	0.0	0.0	0.0	6.7	6.7
Urticaria	0.9	0.0	0.0	0.0	0.0	6.3	6.3	0.0	0.0	0.0	0.0	0.0	0.0
Crevice	0.9	0.0	0.0	0.0	0.0	0.0	0.0	0.0	0.0	0.0	0.0	6.7	0.0
Heloma	0.9	0.0	0.0	0.0	0.0	0.0	0.0	0.0	0.0	0.0	0.0	6.7	6.7
(14.5-29.6 km)			Female			Male							

		Tier	ra %	Set	t %	Cott	on %	Tier	a %	Se	et %	Cott	on %
Muscle lesion	%Tt.	RF	LF	RF	LF	RF	LF	RF	LF	RF	LF	RF	LF
Pain due inadequate warm	11.2	15.4	4.0	4.0	7.7	0.0	12.5	10.5	0.0	5.3	10.5	0.0	0.0
Inflammation	0.9	0.0	4.0	4.0	0.0	0.0	0.0	0.0	0.0	0.0	0.0	0.0	0.0
Muscle discomfort	0.9	0.0	0.0	0.0	0.0	0.0	0.0	0.0	0.0	5.3	0.0	0.0	0.0
Sprain	0.9	0.0	0.0	4.0	0.0	0.0	0.0	0.0	0.0	0.0	0.0	0.0	0.0
(14.5-29.6 km)				Fem	ale					N	Iale		

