(14.5-29.0 KIII)		Tier	ra %	Set	t %	Cott	on %	Tierr	a %	Se	et %	Cott	on %
Nail lesion	%Tt.	RF	LF	RF	LF	RF	LF	RF	LF	RF	LF	RF	LF
Onychocryptosis	0.9	7.7	0.0	0.0	0.0	0.0	0.0	0.0	0.0	0.0	0.0	0.0	0.0
Subungual hematoma	1.9	0.0	0.0	0.0	0.0	6.3	6.3	0.0	0.0	0.0	0.0	6.7	6.7

Km=Kilometres, %=Percentage, Tt=Total, RF=Right foot, LF=Left foot.

In the second part of the hike, a greater variety of dermal lesions was detected. The most prevalent were blisters, erosions and reddened skin. Again, no urticaria, reddened skin, crevices, or helomas were detected with either technical sock. Differences were found between the percentage of dermal lesions among hikers wearing technical socks (21.1%) or non-technical socks (54.8%) (p-value=0.001). By gender, the percentage of women and men with dermal lesions was higher among wears of non-technical socks (women 68.8% and men 40%) than among wearers of technical socks (women 26.3% and men 15.8%) but the differences only were significant in women (p-value=0.006). Considering the sock used in each foot, in the case of women, presented more reddened skin in both RF and LF if they used cotton sock compared to the Tierra and Set (RF and LF p-values=0.023). In the case of men, they presented more blisters in the LF if they used Set sock than cotton or Tierra (p-value=0.021) and more erosion in the RF if they used cotton sock in comparison with the Tierra or Set (p-value=0.018) (Table 4). A greater variety of total muscle lesions was also detected in the second part of the hike: pain due to inadequate warm, inflammation, muscle discomfort and sprain. No differences were found between any of the muscular injuries analysed and the technical and non-technical socks neither by sex (Table 4).

Nail lesions like onychocryptosis (0.9%) and subungual hematomas (1.9%) were infrequently and developed only in the second part of the hike. No difference between any of the nail lesions analyzed and technical and non-technical socks were found. By sex, no differences were found (Table 4).

The temperature comparisons between technical and non-technical socks, regardless of distance, foot, measurement area and sex, showed significant differences. The Friedman test was performed (p value <0.005) for the comparisons between paired samples and the Kruskal-Wallis test was performed (p value <0.009) for independent samples. (Supplementary data, tables A, B).

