The study of the perimeter of hikers' feet analysed in total and by gender, in relation to distance and sock type, did not reveal significant results (data not shown).

Table 7. Probability of suffering skin and muscle lesions in relation to anthropometric variables and sock type throughout the hike.

1	PROBABILITY SKI	N LESIONS	PROBABILITY M	USCLE LESIONS		
Dist	ance:	Distance: 14.5-29.6 Km	Distance: 0-14.5 Km			
96% If	female	90% If male	100% I	f male		
100% If non-	technical sock	100% If non-technical sock	67% If non-te	chnical sock		
Direct relation	Inverse relation	Inverse relation	Direct relation	Inverse relation		
BMI	Age	Age	BMI	Age		

km=Kilometre, %= Percentages, BMI=Body mass index.

It was possible to study the relation between variables and predict the probability of lesions developing during the hike using logistic regression analysis (Table 7). Women have a higher probability than men of suffering skin lesions in hikes of up to 14.5 km. However, men have a higher probability than women of suffering skin lesions on hikes of 14.5 to 29.6 km and muscle lesions on hikes of up to 14.5 km.

The non-technical socks showed the highest probability of wearers suffering dermal and muscle lesions, both from 0-14.5 km and from 14.5 km to the end of the hike. The probability of dermal and muscle lesions developing in relation to the quantitative variables showed direct and inverse relations. From 0-14.5 km, the BMI and age of hikers are directly and inversely related, respectively, both in dermal and in muscle lesions. In the second part of the hike, age continued to show an inverse relation with skin lesions, but no relation with BMI was identified (Table 7).

Supplementary data

Protocol of Measures. Top shows the protocol of measure at the starting point (0 km). Middle part includes the protocol of the first part of the hike (0-14.5 km) and lower part of the table reflex the measurement protocol of the second part of the hike (14.5-29.6 km)

PPOTOCOI	OF MEASURES
STARTING POINT (0 Km)	OF MEASURES
Dorsal Number: Gender: Gender:	Foot size Weight Size
Body mass index (BMI):	The state of the s
	Previous Alterations on skin, muscles or
nails	
	rature LF
Plantar Plantar	
Dorsal Dorsal	
Perimeters RF: (Three different measures)	Perimeters LF: (Three different measures)
tibia	tibia
hell	hell
toes instep	toes instep
FIRST PART OF THE HIKE (0-14.5 Km)	Perimeters RF: (Three different measures)
	tibia
Temperature RF: (Three different measures)	
Plantar	

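### The comparison of dermal lesions between women and men is uncorrected, non-randomised and tested for the first half only, and the second-half statement that men are at higher risk conflicts with the printed rates

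*Combined protocol and SAP*

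**What the plan says.** Section 3 (study design) gives the objective as the influence of sock type on foot injury. It describes the sample: "The sample comprised 109 participants (53 men and 56 women"). It adds: "Two women had to give up the hike for personal reasons", and says that both of them wore technical socks.

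Section 6 (statistical tests) treats the two kinds of variable differently. For quantitative variables: "Friedman's test for related samples and Kruskal-Wallis was performed for independent samples, both with Bonferroni correction for multiple testing was applied". For qualitative variables, which include the lesions, it says only: "chi-square or Fisher's exact test with a significance level of α = 0.05 was carried out".

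The Results make three kinds of statement about sex and dermal lesions:

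- **First half, text after Table 3:** "The women had a higher percentage of dermal lesions (23.2%) than the men (7.5%) (p-value=0.034), regardless of sock type".
- **Second half, text after Table 4:** rates by sex within sock group, in per cent. These are "women 68.8% and men 40" for non-technical socks and "women 26.3% and men 15.8" for technical socks. Socks are compared within each sex; women are not compared with men.
- **Logistic regression, text below Table 7:** "Women have a higher probability than men of suffering skin lesions in hikes of up to 14.5 km". The next sentence says that men have the higher probability from 14.5 to 29.6 km, and Table 7 shows 90% for male in that column. No odds ratio, confidence interval or p-value accompanies either statement.

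**The concern.** The women-versus-men comparison is secondary and concerns a factor that nobody randomised. It is tested at the full 0.05, one of many lesion tests by sex, foot and sock, and is presented as a finding. The parallel second-half comparison can be computed from the printed rates but is not shown.

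The omission matters because of what stands in its place. The only second-half statement comparing the sexes is the regression sentence, which reverses the direction. A reader would conclude that women are at greater risk early and men late. The second-half rates show women higher in both sock groups, and the missing comparison would have made that conflict visible.

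**Working it through.** **Inputs.** Enrolled: 56 women, 53 men (section 3). Sock groups from Table 1: women 38 technical and 18 cotton; men 38 and 15. The percentages come from the Results text. Section 6 does not state sidedness; two-sided tests are assumed.

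**1. Reproduce the printed first-half p-value.** 23.2% of 56 is 13; 7.5% of 53 is 4.

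- Two-sided Fisher, 13/56 against 4/53: p=0.0337, which is the printed 0.034.
- Pearson: 109 × (13×49 − 43×4)² / (56×53×17×92) = 5.08, p=0.0242.
- Yates-corrected: p=0.047.

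Two-sided Fisher also reproduces the printed sock comparisons of 0.002 (women, first half: 9/18 against 4/38), 0.001 (all, second half: 17/31 against 16/76) and 0.006 (women, second half: 11/16 against 10/38). Counts and test are therefore well identified.

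**2. Rebuild the second half.** With two women withdrawn, 54 women and 53 men remain.

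| Sock | Women | Men |
|---|---|---|
| Technical | 10/38 (26.3%) | 6/38 (15.8%) |
| Cotton | 11/16 (68.8%) | 6/15 (40%) |
| Total | 21/54 (38.9%) | 12/53 (22.6%) |

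The sock totals, 16/76 and 17/31, match the printed 21.1% and 54.8%. Women against men: Fisher p=0.094, Pearson p=0.069.

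**3. Denominator check.** The women's denominators of 38 and 16 are the only ones that fit 26.3% and 68.8%. Section 3 says both withdrawals wore technical socks, which would give 36 and 18; the nearest values would then be 25.0% or 27.8%, and 66.7% or 72.2%. The passages disagree. With 20 to 22 affected women of 54, Fisher p runs from 0.14 to 0.06; it takes 23 to fall below 0.05 (0.039).

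**4. Stratify by sock.** Mantel-Haenszel OR = Σ(ad/n) / Σ(bc/n), where a and b are women with and without lesions, and c and d are men with and without.

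- First half, women 4/38 and 9/18, men 1/38 and 3/15: (4×37/76 + 9×12/33) / (34×1/76 + 9×3/33) = 5.220/1.266 = 4.1 (95% CI 1.1 to 14.9); p=0.026, or 0.051 with continuity correction. Stratum odds ratios: 4.35 technical, 4.0 cotton; homogeneity p=0.95.
- Second half: (10×32/76 + 11×9/31) / (28×6/76 + 5×6/31) = 7.404/3.178 = 2.3 (0.95 to 5.7); p=0.063.

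**5. Allow for two looks.** Two independent tests at 0.05 carry a family-wise rate of 1 − 0.95² = 0.0975. Doubling the first-half p (Bonferroni; Holm gives the same for the smaller p-value):

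| First-half test | p | Doubled |
|---|---|---|
| Pearson | 0.0242 | 0.0485 |
| Mantel-Haenszel, uncorrected | 0.0255 | 0.051 |
| Fisher | 0.0337 | 0.067 |

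The second-half result is above 0.05 before any correction. With one fewer affected woman in the first half (12/56), Fisher p is 0.057.

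**The case against.** **The first-half result may survive correction.** Section 6 allows chi-square or Fisher. The smallest expected count is 17×53/109 = 8.3, so chi-square is valid, and its doubled p-value is just under 0.05. A likelihood-ratio test from a sock-adjusted logistic model on the same counts gives 0.021, doubled 0.042. The documents define no two-test family either; that choice is mine. This stands: a reader might infer that nothing survives correction, but the answer depends on the test. Borderline is the accurate word.

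**The qualifier about sock type is sound.** A reader might infer that it is wrong, because neither stratum is significant alone (Fisher p 0.36 technical, 0.15 cotton). With 5 and 12 events that is a lack of power, not evidence against a common effect. The stratum odds ratios are nearly equal and the pooled interval excludes 1. This stands; what is missing is the stratified estimate.

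**The second half is not wholly unreported.** The rates by sex within sock are printed, and the regression does speak to sex. Only the direct comparison is absent. A reader might infer that it was dropped because it missed 0.05; the documents give no reason for its absence.

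**The regression may be adjusted for other variables.** Table 1 gives women a mean age of 36 and men 49, and Table 7 reports an inverse relation with age. Adjustment for age could shift the sex effect towards men, so the crude and sock-stratified rates do not prove the regression wrong. But the covariates and estimate are not given, so the reversal cannot be checked.

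**Conclusion.** The point holds as a reporting and interpretation problem about sex; it does not touch the sock-type result. The first-half difference is real in the data (23.2% against 7.5%) and consistent across socks, but it is a borderline, uncorrected comparison of a non-randomised factor. The second half points the same way, with a smaller and overlapping odds ratio (2.3 against 4.1), and is not significant. A higher risk in women is suggested, not established.

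Two further readings go too far. One is that the documents confine the sex effect to the first 14.5 km: they claim a reversal afterwards. The other is that the non-significant second half refutes the first: its direction agrees. The least supported statement is the reversal, so deleting only the first-half sentence would leave the weaker claim standing.

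This rests on counts rebuilt from rounded percentages, on two-sided tests, and on second-half denominators that conflict with section 3. Counts of 20 to 22 affected women leave the conclusion unchanged.

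**What to change.** - Report women against men for both halves, with counts and sock-stratified Mantel-Haenszel odds ratios: 4.1 (95% CI 1.1 to 14.9) and 2.3 (0.95 to 5.7).
- Label the comparison exploratory. Say that the first-half result is borderline once two looks are allowed for (doubled p 0.0485 by Pearson, 0.067 by Fisher).
- Word the first-half direction as suggested, in the text after Table 3 and below Table 7. The qualifier about sock type may stay if the stratified estimate is given beside it.
- Reconcile the second-half sex statement in Table 7 and the text below it with the rates after Table 4. Give the regression odds ratio, confidence interval and covariates, or withdraw the claimed reversal.
- Reconcile the women's second-half denominators (38 technical, 16 cotton) with the sock type recorded for the two withdrawals.

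The cost is a few lines of analysis on existing data and some rewording. The downside is that the sex difference becomes a suggestion and no longer a significant finding.

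### The women's first-half blister p-values (RF 0.050, LF 0.042) do not reproduce from Tables 1 and 3, and the six sex-by-foot sock-model results have no stated multiplicity correction

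*Combined protocol and SAP*

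**What the plan says.** Section 6 (Statistical tests) describes two regimes. For the quantitative variables, Friedman and Kruskal-Wallis tests are used, "both with Bonferroni correction for multiple testing was applied". For the qualitative variables, which include all lesions, the "chi-square or Fisher's exact test with a significance level of α = 0.05 was carried out". No correction is named for the lesion tests. Section 6 does not say how many groups each test compares, or when chi-square gives way to Fisher.

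The Results report six differences between sock models within sex and foot:

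- First half, women: more blisters on each foot "when they wore cotton sock compared to the Tierra and Set socks (RF p-value = 0.050, LF p-value = 0.042").
- Second half, women: more reddened skin on each foot "if they used cotton sock compared to the Tierra and Set (RF and LF p-values=0.023").
- Second half, men: "they presented more blisters in the LF if they used Set sock than cotton or Tierra (p-value=0.021").
- Second half, men: "more erosion in the RF if they used cotton sock in comparison with the Tierra or Set (p-value=0.018").

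For men in the first half, the Results say "there was no difference in any of the skin lesions at 14.5 km on any foot compared to the sock used (Table 3"). By-foot tests beyond these six were therefore run.

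**The concern.** The counts behind each row can be rebuilt from the tables, so the printed p-values can be checked. Two of the six fail the check. One of them, 0.050, is already not below the stated 0.05, yet it is set beside the LF result as a finding and contrasted with no difference in men. The lesion tests are also repeated over sex, foot, half of the hike and lesion type, each at 0.05. Whether the six hold as findings therefore depends on a method and a family that the document does not state.

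**Working it through.** **Inputs.** Women's denominators (Table 1; Tierra, Set, cotton) are RF 13, 25, 18 and LF 25, 13, 18. Blister percentages (Table 3) are RF 0.0, 8.0, 22.2 and LF 4.0, 7.7, 27.8. The counts are therefore RF 0/13, 2/25, 4/18 and LF 1/25, 1/13, 5/18, and each rounds back to the printed percentage. Tests are taken as two-sided, since sidedness is not stated.

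**Step 1: reproduce the plan's other four values.** With three groups and a yes/no outcome, Pearson is X² = Σ(x − nP)² / [nP(1 − P)], where P is the overall proportion. On 2 degrees of freedom, p = exp(−X²/2).

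| Row (second half) | Tierra, Set, cotton | X² | p | Printed |
|---|---|---|---|---|
| Women RF reddened skin | 0/13, 0/25, 3/16 | 7.544 | 0.0230 | 0.023 |
| Women LF reddened skin | 0/25, 0/13, 3/16 | 7.544 | 0.0230 | 0.023 |
| Men LF blister | 0/19, 4/19, 0/15 | 7.742 | 0.0208 | 0.021 |
| Men RF erosion | 0/19, 0/19, 3/15 | 8.056 | 0.0178 | 0.018 |

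All four match, so the reconstruction and the test are calibrated.

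**Step 2: apply the same test to the blister rows.**

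- RF: P = 6/56, X² = 1.560 + 0.193 + 2.492 = 4.244 (unrounded sum), p = 0.120. Printed: 0.050.
- LF: P = 7/56, X² = 1.651 + 0.275 + 3.841 = 5.767, p = 0.056. Printed: 0.042.

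**Step 3: try the other permitted forms.** Pooling the technical models gives RF 2/38 v 4/18 and LF 2/38 v 5/18.

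| Form | RF | LF |
|---|---|---|
| Three-group Pearson | 0.120 | 0.056 |
| Three-group exact | 0.122 | 0.072 |
| Pooled v cotton, Fisher | 0.077 | 0.029 |
| Pooled v cotton, Pearson uncorrected | 0.055 | 0.017 |
| Pooled v cotton, continuity-corrected | 0.146 | 0.052 |
| Tierra v cotton, Fisher | 0.120 | 0.067 |
| Tierra v cotton, Pearson uncorrected | 0.069 | 0.026 |
| Set v cotton, Fisher | 0.218 | 0.359 |
| Printed | 0.050 | 0.042 |

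No row gives either printed value. RF is never below 0.05. Between the three-group and pooled forms, LF is below 0.05 only when pooled (Fisher or uncorrected Pearson). The Tierra-only 0.026 is not the contrast that the sentence describes, and its Fisher value is 0.067.

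**Step 4: multiplicity over the six reported differences.** The Bonferroni limit is 0.05/6 = 0.0083.

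- Printed values: the smallest is 0.018, and 6 × 0.018 = 0.108. Holm also gives 0.108 for all six.
- Three-group Pearson: smallest 0.0178, adjusted 6 × 0.0178 = 0.107.
- Three-group exact: smallest 0.0194, adjusted 6 × 0.0194 = 0.116.
- Fisher on the contrast as worded: smallest 0.0132, adjusted 6 × 0.0132 = 0.079.

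None passes Bonferroni or Holm on these values.

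**Step 5: how far this depends on the method.** Benjamini-Hochberg on the printed values gives 6 × 0.023/4 = 0.0345 for the four second-half rows and 0.050 for the two blister rows. With the blister rows recomputed by three-group Pearson, the four stay at 0.0345 and the blister rows become 0.067 (LF) and 0.120 (RF). On three-group exact values the smallest Benjamini-Hochberg value is 0.051. On Fisher values, five of the six have 0.034 to 0.035. Uncorrected two-group Pearson gives 0.0045 to 0.0060 for the four second-half rows. These pass Bonferroni (6 × 0.0060 = 0.036), and under Holm LF blisters pass too (2 × 0.017 = 0.034). The smallest expected counts in those four tables are only 3 × 16/54 = 0.89 (each reddened-skin row), 4 × 19/53 = 1.43 and 3 × 15/53 = 0.85.

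**The case against.** The strongest reply has four parts.

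1. **The multiplicity result depends on the test.** Section 6 permits chi-square, and uncorrected two-group Pearson passes four rows under Bonferroni and five under Holm. This stands as a limit. A reader might infer that the six results fail every correction; the documents do not support that. However, with expected counts near 1 the uncorrected test is unsuitable, and it does not produce the printed values.
2. **The LF result is not exaggerated.** The sentence contrasts cotton with both technical models. Read as a pooled contrast, Fisher gives 0.029, stronger than the printed 0.042. This stands: the LF value needs correcting and its contrast stating, but the result need not be withdrawn.
3. **The blister sentence does not itself use the word significant.** This is true, and 0.050 is not below 0.05. The sentence nevertheless follows directly on a significant per-woman comparison and introduces the blisters as its particular case.
4. **The family is the reviewer's construction, and the rows are correlated.** This stands in part. The six are those reported. Counting the non-significant by-foot tests would be stricter, but the document does not list them, so any larger count is an assumption and none is relied on here.

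Isolated routes towards the printed figures exist, but each needs something the document does not describe. RF reaches 0.045 with a linear trend test. It reaches 0.050 with a mid-p test if there were 11 Tierra women. LF reaches 0.042 with a likelihood-ratio test if there were 16 cotton women, which contradicts the printed 27.8%.

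**Conclusion.** The point holds. Neither printed blister p-value follows from the document's own tables by a permitted chi-square or Fisher form. By the test that reproduces the other four, both exceed 0.05 (0.120 and 0.056). RF has no nominal support; LF has it only under a pooled contrast that should be stated. The six sex-by-foot results have no stated correction, and on printed, three-group or Fisher values none passes Bonferroni or Holm over six tests. Less strict procedures give mixed answers.

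A reader might go further and infer that cotton made no difference to women's blisters, or that the main result is undermined. The tables support neither. Cotton has the highest blister percentage on both feet in women. The pooled per-hiker comparison remains strong: the Results percentages correspond to 12/33 v 5/76 in the first half (Fisher 0.0002) and 17/31 v 16/76 in the second (Fisher 0.001).

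The conclusion assumes two-sided tests and the Table 1 denominators for the first half. One separate matter needs reconciling. Table 4's percentages imply 16 cotton women, against 18 in Table 1, while section 3 says of the two women who gave up that "Both wore technical socks". This affects the second-half rows, not the blister values.

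**What to change.** - Replace 0.050 and 0.042 with correctly computed values, and state the test and contrast. Given the sparse counts, use Fisher or an exact test: pooled against cotton gives 0.077 (RF) and 0.029 (LF); three-group exact gives 0.122 and 0.072.
- Do not present the women's RF blister difference as significant. Keep the LF result only with the pooled contrast named.
- Label the six sex-by-foot sock-model results exploratory, or apply Bonferroni or Holm to a named lesion family with its number of tests.
- Rest the conclusion on the pooled per-hiker technical versus non-technical comparison already reported.

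The cost is re-running existing tests on existing data and editing two paragraphs of the Results, plus a sentence in section 6. The downside is that the subgroup claims become less definite. Bonferroni over correlated, sparse tests is conservative, so a real difference between sock models could be missed.

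### The sock effect on skin lesions is called significant only in women, but no sock-by-sex test is reported and the men's first-half any-lesion result is not printed

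*Combined protocol and SAP*

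**What the plan says.** The Statistical tests section gives one rule for qualitative variables: "chi-square or Fisher's exact test with a significance level of α = 0.05 was carried out". It also mentions logistic regression, but no sock-by-sex interaction.

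**First part of the hike (0-14.5 km).** The Results compare "hikers wearing technical socks (6.6%) and non-technical socks (36.4%) (p-value=0.000"). They then state that "the percentage of women with dermal lesions was significantly higher among wearers of non-technical socks (50"%), against 10.5% in technical socks, p=0.002. For men the text says that "there was no difference in any of the skin lesions at 14.5 km on any foot compared to the sock used" and refers to Table 3, which is broken down by lesion and foot. The men's any-lesion percentages by sock and their p-value are not printed.

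**Second part (14.5-29.6 km).** The overall comparison is of "hikers wearing technical socks (21.1%) or non-technical socks (54.8%) (p-value=0.001"). By sex, the text sets "wears of non-technical socks (women 68.8% and men 40"%) against "wearers of technical socks (women 26.3% and men 15.8"%), and adds "but the differences only were significant in women (p-value=0.006"). The men's p-value is not printed.

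**The concern.** Whether the sock effect differs between women and men is a question about the difference between two effects. It is not answered by seeing which sex falls below 0.05. The any-lesion counts are small, especially among men: 4 men with lesions in the first half and 12 in the second, in groups of 15 and 38. A non-significant result in men would therefore be unsurprising even if a real effect were present.

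The first half adds to the problem because the women's hiker-level result is printed and the men's is not. What stands in its place for men is a set of tests on single lesions on single feet. By Table 3 these rest on two feet (right-foot blister), three feet (left-foot blister), one foot (right-foot erosion) and none (left-foot erosion). Such tests could hardly detect anything.

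Skin lesions by sock type are central to the stated objective. At stake is what a reader may conclude about men.

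**Working it through.** **Inputs.** Group sizes come from Table 1: men 15 cotton and 38 technical (19+19); women 18 cotton and 38 technical (25+13). Percentages come from the Results. Tests are taken as two-sided, because the documents do not state sidedness.

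**Counts, first half.**
- Cotton overall: 36.4% of 33 = 12. Women: 50% of 18 = 9. Men: 12-9 = 3 of 15 (20.0%).
- Technical overall: 6.6% of 76 = 5. Women: 10.5% of 38 = 4. Men: 5-4 = 1 of 38 (2.6%).
- Check: men in total 4/53 = 7.5%, as printed.

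**Counts, second half.**
- Women: 68.8% = 11/16 and 26.3% = 10/38. Men: 40% = 6/15 and 15.8% = 6/38.
- Check: 17/31 = 54.8% and 16/76 = 21.1%, as printed. The women's cotton entries in Table 4 (25.0, 12.5, 18.8, 6.3) are also sixteenths.

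**Reproducing the printed p-values (Fisher's exact test).**

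| Comparison | Counts | Computed | Printed |
|---|---|---|---|
| Women, second half | 11/16 vs 10/38 | 0.0057 | 0.006 |
| Women, first half | 9/18 vs 4/38 | 0.0021 | 0.002 |
| All, second half | 17/31 vs 16/76 | 0.0011 | 0.001 |
| All, first half | 12/33 vs 5/76 | 0.0002 | 0.000 |
| Women vs men, first half | 13/56 vs 4/53 | 0.0337 | 0.034 |

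All five agree, so the counts and the test used are well supported.

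**Effects by sex.** OR = ad/(bc), cotton versus technical.
- First half, women: (9×34)/(9×4) = 8.50 (95% CI 2.12-34.06), p=0.002.
- First half, men: (3×37)/(12×1) = 9.25 (0.88-97.48), p=0.064.
- Second half, women: (11×28)/(5×10) = 6.16 (1.71-22.16), p=0.006.
- Second half, men: (6×32)/(9×6) = 3.56 (0.92-13.74), p=0.076.

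**Interaction on the odds-ratio scale.** The variance of the log ratio of ORs is the sum of the reciprocals of all eight cells.
- First half: 8.50/9.25 = 0.92; variance 0.502+1.444 = 1.945, SE 1.395; 95% CI 0.06-14.1; p=0.95.
- Second half: 6.16/3.56 = 1.73; variance 0.427+0.476 = 0.902, SE 0.950; 95% CI 0.27-11.1; p=0.56.

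**Interaction on the risk-difference scale.**
- First half: 39.5 points in women, 17.4 in men; difference 22.1, p=0.18.
- Second half: 42.4 and 24.2; difference 18.2, p=0.35.

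**Sex-adjusted sock effect.** Mantel-Haenszel OR = Σ(ad/n)/Σ(bc/n).
- First half: (306/56 + 111/53)/(36/56 + 12/53) = 7.559/0.869 = 8.7 (2.6-28.7).
- Second half: (308/54 + 192/53)/(50/54 + 54/53) = 9.326/1.945 = 4.8 (1.9-12.1).

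**Power in men.** At the men's own observed rates, exact Fisher power with 15 vs 38 is about 43% in the first half and 41% in the second.

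**The case against.** The strongest reply is that the text is more careful than the short quotation suggests. The second-half sentence reports more lesions with non-technical socks in both sexes, prints the men's 40% and 15.8%, and limits only statistical significance to women. Under Fisher's test that is true. The first-half any-lesion text makes no women-only claim. The overall comparisons and the closing logistic-regression text (Table 7) report sock effects without limiting them to one sex. All of this stands. A reader might infer that the documents claim a benefit for women only; they do not say so.

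A reader might also infer from the similar odds ratios that the effect is the same in both sexes. That is not shown either. The first-half comparison rests on one lesion among 38 men in technical socks. The second-half odds ratio is lower in men, and the absolute differences are larger in women in both halves.

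Nor can the men's first-half result be called significant. An uncorrected chi-square gives p=0.031, but the smallest expected count is 15×4/53 = 1.1. Fisher is the suitable test, and it is the one that reproduces the printed p-values.

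Table 7 does not settle the matter. It lists sex and sock type but prints no odds ratios, intervals or model terms, so neither adjustment for sex nor an interaction can be confirmed from it.

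**Conclusion.** The point holds for the sex-specific reading only. Separate within-sex tests are set side by side, no sock-by-sex test is reported, and the men's first-half any-lesion result (20.0% vs 2.6%) is missing while the women's is printed. The data give no evidence that the sock effect differs by sex: interaction p is 0.95 and 0.56 for odds ratios, and 0.18 and 0.35 for risk differences. They do not establish equality, since the ratio of odds ratios could lie anywhere from 0.06 to 14.1 in the first half and 0.27 to 11.1 in the second. The pooled sock effects are unaffected.

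The counts are rebuilt from rounded percentages. The second-half women's counts carry one unresolved conflict: 68.8% and 26.3% need 16 cotton and 38 technical, which puts both withdrawals among cotton wearers, whereas the study design section says both women who withdrew wore technical socks. With 18 and 36, neither percentage can be obtained (12/18 = 66.7%; 9/36 = 25.0%; 10/36 = 27.8%). The nearest such counts give women's ORs of 6.00 or 5.20 and ratios to the men's OR of 1.69 or 1.46, so the conclusion does not depend on how this is resolved.

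**What to change.** 1. Print the men's first-half any-lesion result (3/15 vs 1/38) and both men's Fisher p-values (0.064 and 0.076), with intervals.
2. For each section, report one sex-adjusted sock effect (Mantel-Haenszel OR 8.7, 2.6-28.7; and 4.8, 1.9-12.1) and the sock-by-sex interaction estimate with its interval.
3. Replace the second-half significance statement, or follow it, with a sentence saying that a sex difference in the sock effect was not shown.
4. Reconcile the second-half women's denominators with the account of the two withdrawals, and confirm the counts from the source data.

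This takes a few lines of re-analysis and some rewording, with no new data. The small cost is that the interaction intervals are wide and must be shown.
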